4.2 Follow-up procedures

There will be no scheduled follow-up; however, participants will be given the contact information of the PI and study physician and instructed to contact us if they experience any side effects or discomfort following the study.

4.3 Subject Completion/ Withdrawal procedures

If a participant wishes to discontinue their participation in the study before it ends, they will receive \$25 for each hour that they participated. Upon completion of the study, they will receive \$125.

5. STUDY EVALUATIONS AND MEASUREMENTS (how measurements will be made)

Details of Heartbeat Detection Task: We will use the well-validated Heartbeat Detection Task (Barrett et al., 2004; Kleckner et al., 2016) to provide an index of participants' interoceptive sensitivity (i.e., how aware they are of physiological changes in the body). To do so, we will first prepare the participant for psychophysiology data collection. Participants are given the chance to go to the restroom if need be and get comfortable before we attach the sensors. Female research assistants will be assigned to female participants, while both male and female research assistants will be assigned to male participants, in an effort to reduce participant discomfort with the procedure of attaching the sensors. Only three sensors will be attached for this task as is standard for basic EKG measurement. One sensor will go on the participant's right collarbone, and two more sensors right below their ribs. Once sensors have been attached, we will collect 5 minutes of baseline data while the participant sits and relaxes. This baseline is important for us to help generate participant-specific trials for the heartbeat detection task itself. Next, participants will either complete the heartbeat detection task or our questionnaire measures of conceptual knowledge. These two tasks are counterbalanced because we suspect that the activation of interoceptive concept knowledge could temporarily elevate interoceptive sensitivity--and likewise, interoceptive sensitivity could activate interoceptive concept knowledge. Therefore, counterbalancing each task should help reduce order effects. For the heartbeat detection task, we use MATLAB to automatically generate a person-specific heartbeat task based on their baseline cardiac data. Participants put on headphones and follow the on-screen instructions provided to them. They are instructed to listen for a series of 3 beeps in their headphones then must indicate on the computer whether these beeps occurred *between* their current heartbeats or *during* their current heartbeat. Participants also rate how confident they are in their response. Participants have 2 practice trials with the research assistant to ensure they understand the task, and then complete the 60 target trials on their own in the private, quiet lab room. Accuracy is computed by comparing participant's hits and misses, and determining if they were accurate above chance. After both the heartbeat detection and conceptual knowledge tasks are done, the experimenter will help the participant remove the psychophysiology sensors. The sensors must stay on across both tasks since they are counterbalanced and we wish to keep all psychological factors as equal as possible.

Details of the Trier Social Stress Task (TSST). The TSST is a commonly-used acute stress test to measure psychological and biological responses to stress in the laboratory. In this task, participants will be asked to prepare for and give a 10-minute speech and complete a difficult mental arithmetic task as they are evaluated by trained interviewers. The nature of the task is stressful and participants may experience varying levels of stress, anxiety, and possibly embarrassment. The consent form at the beginning of the study describes that they will take part in a "role play" during a cognitive performance task. We describe the task in this vague way in the initial consent because we want to ensure that the baseline physiology data is clean and not impacted by participants' anticipatory stress about the upcoming task. Additionally, prior to the participant's participation in the TSST, participants will be informed in greater detail about the procedure for TSST, and they will be asked if they would like to continue. If they do continue, but wish to stop at any time, they will be reminded that they can.

After being informed of the procedures and confirming participants would like to continue, the experimenter will introduce two more research assistants who will act as the interviewers/judges. Participants will have 2 minutes to prepare for the speech, in which they will be asked to answer why they are the perfect candidate for their dream job. Participants will then give a 10-minute speech in front of the two interviewers

and a video camera. After the 10-minute speech, participants will complete a verbal math task for 5 minutes. While participants are completing the tasks, interviewers will remain neutral (give neither positive nor negative feedback). The experimenter leading Session II will also be present throughout, to help with timing the tasks, etc.

Biomarker Information:

Saliva Samples. We will take 4 saliva samples during the study via the passive drool method. Passive drool is a saliva collection method for collecting whole saliva. Passive drool is considered by many researchers to be the gold standard when collecting saliva samples for biological testing, because it provides the purest sample possible and allows researchers to "biobank" samples for testing. Participants allow saliva to pool in mouth, then, with head tilted forward, gently force saliva through a small straw and into the vial. Participants will be aided by trained research assistants wearing rubber gloves. About 2ml of saliva will be collected at each sampling time. Saliva samples will be assayed for levels of the stress hormone, cortisol, as well as another HPA axis byproducts including ACTH and testosterone.

Blood Samples. We will draw 10 mL of blood into vacutainer EDTA tubes at each time point, which will be stored on ice for the duration of the study, and then centrifuged to isolate plasma and stored in 1 mL aliquots in cryovials in a -80 degree freezer until the study is complete. Samples will then be assayed for levels of pro-inflammatory cytokines (i.e., interleukin-6, tumor necrosis factor alpha, interleukin-1) using multiplex bead-based assays.

Psychophysiology. We will collect electrocardiogram and impedance cardiography data from participants to examine how propranolol and exposure to the TSST influence autonomic physiology.

Questionnaires (for exploratory moderator analyese):

Demographics.

We ask participants' age, gender, race/ethnicity, weight/height (to calculate BMI), perceived SES, and also about participants' comfort with giving speeches / being the center of attention.

Health Behavioral Questionnaire ([name], 2016). This asks a series of questions to make sure that participants followed instructions prior to the session and are still eligible to participate. It includes items "Which medications have you taken in the last 48 hours?"

UCLA Loneliness Scale: (Russell, D., Peplau, L.A., and Ferguson, M.L 1978) This is a commonly used, 10 item, measure of loneliness.

The PHQ-9: (Spitzer, 1999) This a multipurpose, validated instrument for screening, diagnosing, monitoring and measuring the severity of depression.

Perceived Stress Scale: (Cohen, 1994) This is a widely used psychological instrument for measuring the perception of stress; i.e the degree to which situations in one's life are appraised as stressful.

Social Provisions Scale (Cutrona, C. E. and Russell, D., 1987). This examines the degree to which respondent's social relationships provide various dimensions of social support.

Fear of Evaluation Scale (Leary 1983). This is a 30-item, self-rated scale used to measure social anxiety.

State-Trait Anxiety Inventory (Spielberger 1983) this inventory has 40 self-report items pertaining to anxiety affect.

The MacArthur Scale of Subjective Social Status: (Adler, 1984) This is a commonly used measure subjective social status. In an easy pictorial format, it presents a "social ladder" and asks individuals to place an "X" on the rung on which they feel they stand. There are two versions of the ladder, one linked to traditional SES indicators and the second linked to standing in one's community, in this case UNC. We will give them both. It is useful to be able to make comparisons between objective and subjective SES.

Parent SES: This is a six item questionnaire to assess the socioeconomic status of the participant and their family. It will be used to make comparisons between objective and subjective SES.

PANAS-circumplex questionnaire. Participants rate which emotions they felt during the TSST and also how they are feeling currently. Participants rate how intensely they felt those emotions using a Likert

scale. Additionally, participants report how clear their emotions were during the TSST. This is our measure of discrete emotion, perceived emotional intensity, and perceived emotional clarity.

Somatic Sensations questionnaire. Participants rate which somatic sensations they felt during the TSST and also rate how clearly / distinctly they experienced those bodily changes. Participants use Likert scales for their ratings. We will also assess the participants' feelings about the interviewers using standardized measures.

Challenge threat appraisals: Blascovich, J. & Mendes, W. B. (2000). This questionnaire taps into the degree to which the participant views new experiences as a potential challenge or threat.

6. STATISTICAL CONSIDERATION

[name] and her trainees will be responsible for statistical computations and data analysis. She will consult with colleagues in the Quantitative Psychology area of the Department of Psychology and Neuroscience as needed. All hypothesis tests will be evaluated using 95% confidence intervals, corresponding to a *p* value or .05. Only tests that indicate a *p* value of .05 or less will be considered statistically significant; tests above this *p* value will not be interpreted.

6.1 Primary Endpoint- Statistical Methods

Primary Objective 1. To examine if blocking sympathetic nervous system activity via the beta-blocker propranolol will attenuate inflammatory responses to stress.

Analysis Plan. To address this aim, we will first examine if there was a change in inflammation simply as an effect of taking the propranolol (before stress induction). As such, we will conduct a multilevel model (MLM) examining levels of inflammation (IL-6), with time (BL vs. pre-TSST) as a within-subjects factor and condition (propranolol vs. placebo) as a between-subjects factor. If the result of this test shows a significant interaction, then we will only include the pre-TSST time point in subsequent models. If non-significant, we will use both baseline time points in subsequent analyses. Next, we will conduct an MLM examining levels of inflammation, with time (BL and/or pre-TSST, 30-, 60-, 90-min post-TSST) as a within-subjects factor and condition (propranolol vs. placebo) as a between-subjects factor. We hypothesize that individuals in the placebo condition will show an increase in levels of inflammatory markers from pre- to post-TSST, while those in the propranolol condition will show significantly lower levels of inflammation over time compared to the placebo condition (i.e., no stress-related increase in inflammatory markers).

All outcomes will first be examined using histogram and scatterplot for assumptions of normality and homoscedasticity. Any variables that need to be log-transformed (e.g., cortisol, sAA, IL-6) will be before analyses are run. Across all models, we will evaluate if we need to control for sex, BMI, and objective SES.

Prior to analyses, we will also examine each outcome for outliers existing +/- 3 SDs from the mean within each time point within each condition. Outliers are excluded only within the time point where they were problematic but retained elsewhere to reduce data loss.

All data will be analyzed in R using the lme4 package. As time points are nested within individuals, we take a multilevel modelling approach with the inclusion of a random intercept to model individual differences in each outcome.

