Study Design	This is a randomized, double blind, placebo-controlled study of the effects of propranolol on psychological and physiological responses to stress. It will consist of a telephone screening, an initial in-person session when consent will be obtained, and a subsequent longer, intervention session.
Subject Population	Inclusion Criteria 
1. Healthy individuals from the UNC-Chapel Hill community2. Ages 18-25.3. Fluent in English (spoken and written)4. In good overall health. Exclusion Criteria 
1) Presence or history of chronic physical illness (especially disorders with an inflammatory component, such as rheumatoid arthritis, asthma, allergies, or issues that can affect the heart, including low-blood pressure or other heart conditions)2) Presence or history of psychiatric illness (depression, anxiety)3) Any current prescription medication use4) Currently pregnant or planning to become pregnant (self-reported)5) Engagement in a number of health-compromising behaviors that may affect levels of pro-inflammatory cytokines, including cigarette smoking, excessive caffeine intake and sleep disturbance (e.g., working night shifts)6) Body Mass Index (BMI) greater than 30, given that adiposity is known to relate to baseline levels of inflammation;7) Anxiety about or previous history of problems with blood draws (e.g., fainting)8) Any reported heart conditions
Number Of Subjects	95 (45 per condition; we will run 5 “extra” subjects in the case of data loss)
Study Duration	Each subject’s participation will last 5-6 hours. The entire study is expected to last 1-2 years.
Study Phases	(1) Screening : screening for eligibility will occur via telephone interview, and consent will be obtained in-person during a first study session.
Screening	
Study Treatment	
Follow-Up	(2) Intervention : study intervention/experimental treatment will occur during a second study session. Participants will be randomly assigned to take either a single, 40 mg dose of propranolol, or a placebo, and will go through a standardized psychological stress task. Blood draws and saliva samples will be taken throughout, and will be assayed for inflammation and hormones, respectively. (3) Follow-Up : n/a
Efficacy Evaluations	This does not apply, as this is not a true interventional trial. These are healthy participants.

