1.3 Non-Clinical and Clinical Study Findings

Propranolol blocks the effects of epinephrine and norepinephrine by competitively binding to both β_1 - and β_2 -adrenergic receptors in both the peripheral and central nervous system. It was originally used to treat hypertension, approved by the FDA in 1965. Since then it has been FDA-approved for a variety of other indications, including migraine prevention, and essential tremor. It is even approved for certain pediatric conditions. Propranolol is one of the historically most commonly-used prescription medications, and it is generally viewed as a safe, nontoxic medication in the daily dosage range of up to 640 mg, divided into 2-4 doses per day. The 40mg dose to be given here is expected to be well-tolerated, with the most adverse side effect anticipated being the possibility of allergic reaction. Propranolol rarely causes side effects, including: hypotension, insomnia, fatigue, light-headedness, nausea, bronchospasm, dizziness, headache, hyperglycemia, and muscle weakness. Each of these side effects is uncommon at the low, single dosage being utilized in these studies. Moreover, these side effects are not only rare, but also quite mild and rarely prolonged (i.e. < 1-2 hours) when they do occur. If any of these side effects do occur, the subjects will be given a comfortable place to lie down until the symptoms pass, and will be monitored by the CTRC nurse and the project coordinator.

Studies of the pharmacokinetics of propranolol suggest that peak plasma concentrations following a 40 mg dose occur 1-2 hours after administration; as such, we will have participants rest quietly for 1 hour following administration of the medication before the start the stress task. Plasma half-life of propranolol is 3-6 hours, and as such, we will examine our more exploratory aims at the end of the session, which is still within the half-life of the drug.

The study MD will be on-call during all intervention sessions to assess any side effects and prescribe appropriate management as needed, and a CTRC nurse will be present throughout the majority of study procedures. Given that we do not anticipate any serious side effects to occur and that there is currently no data

to suggest that an acute dose of propranolol leads to serious side effects in healthy populations, we believe the facilities at Howell Hall are sufficient to manage the mild, transient side effects that may occur in response to taking propranolol.

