2 STUDY OBJECTIVE

The purpose of this study is to determine if SNS activation is a key physiological mechanism linking psychological stress and inflammation. Thus, we will experimentally-block SNS activation using propranolol, a beta-blocker, and examine if exposure to propranolol attenuates inflammatory responses to a psychological stressor.

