3.1 Study Design

This is a double blind, randomized, placebo-controlled trial of the effects of propranolol on inflammatory responses to psychological stress in healthy participants. We will use a between-subjects manipulation, given that repeated exposures to the stress task may lead to habituation in both psychological and physiological responses, introducing a potential confound in order-effects. It consists of three stages: 1) telephone screening 2) in-person Session I and 3) in person Session II.

Telephone screening. The telephone screening will be conducted by trained research assistants in the Carolina Social Neuroscience and Health Laboratory, under the supervision of the PI. Inclusion and exclusion criteria will be assessed, and study procedures will be described. If participants meet inclusion criteria and are interested in participants, they will be scheduled for Session I.

Study Session I. Session I will last approximately 30-60 minutes. Participants will enter the lab in Howell Hall at UNC-Chapel Hill, meet the research assistant who is running the session, and read through the consent form. Once participants have been given a chance to ask any questions about the consent form and it is clear that they understand the protocol and are comfortable with proceeding, they will sign a copy of the General Consent Form. Next, subjects are informed in greater detail about the procedure for a heartbeat detection task as a measure of their interoceptive or inner bodily awareness. Task descriptions, instructions, and an opportunity to ask questions will be provided to each participant. The heartbeat detection task will take about 20 minutes to complete, and will be administered by trained research assistants. Following completion of the

heartbeat detection task, the experimenter will reiterate to the participant the general purpose of Session II and remind participants of their scheduled date for Session II.

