Upon completion of the baseline psychophysiological measures, participants will complete trait questionnaire measures while they continue to acclimate to the catheter and the laboratory environment. Once 45 minutes has passed (around 1:15 PM), the nurse will draw the first (baseline) blood sample, and participants will be asked to provide the first (baseline) saliva sample. Next, the oral tablet of propranolol or placebo will be administered to the participant by the nurse. Participants will continue completing trait questionnaires and once finished, they will be given neutral reading material (magazines) to read while drug activation takes place. One hour after administration of the medication (or placebo), the nurse will draw a second blood sample, and participants will be asked to provide a second saliva sample. We will also collect another 5 minutes of psychophysiological data.

Next, the Trier Social Stress Task (TSST; Kirschbaum, Pirke, & Hellhammer) procedures will be explained to participants. The TSST is a commonly-used acute stress test to measure psychological and biological responses to stress in the laboratory. In this task, participants will be asked to prepare for and give a 10-minute speech and complete a difficult mental arithmetic task as they are evaluated by trained interviewers. The nature of the task is stressful and participants may experience varying levels of stress, anxiety, and possibly embarrassment. The consent form at the beginning of the study describes that they will take part in a “role play” during a cognitive performance task (see Consent Form). We describe the task in this vague way in the initial consent because we want to ensure that the baseline physiology data is clean and not impacted by participants' anticipatory stress about the upcoming task. Additionally, prior to the participant's participation in the TSST, participants will be informed in greater detail about the procedure for TSST, and they will be asked if they would like to continue. If they do continue, but wish to stop at any time, they will be reminded that they can.

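### With both arms stressed and the only drug-only IL-6 check at 60 minutes, a later drug effect unrelated to stress could be read as attenuation of the stress response

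*Combined protocol and SAP*

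**What the plan says.** The aim is mechanistic. Section 2 states: "The purpose of this study is to determine if SNS activation is a key physiological mechanism linking psychological stress and inflammation". Only drug versus placebo is randomised. The synopsis (Study Phases) has everyone take propranolol "or a placebo, and will go through a standardized psychological stress task", and Section 3.1 gives the reason for a parallel design: "We will use a between-subjects manipulation, given that repeated exposures to the stress task may lead to habituation". Stress itself is never varied.

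Section 6.1 begins with a condition-by-time test on baseline versus pre-stress IL-6: "we will first examine if there was a change in inflammation simply as an effect of taking the propranolol (before stress induction". If that interaction is significant, baseline is dropped from later models; if not, both pre-stress samples stay. The main model then compares the arms over the pre-stress sample(s) and the 30-, 60- and 90-minute post-stress samples. The hypothesis has two parts: a rise on placebo, and lower levels over time on propranolol. The second part is glossed as meaning that no stress-driven rise occurred. Section 6.2 applies the same procedure to every secondary outcome.

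On timing, Section 4.1 (Intervention/Treatment procedures) says "One hour after administration of the medication (or placebo), the nurse will draw a second blood sample", followed by "We will also collect another 5 minutes of psychophysiological data" and then the stress task. Section 1.3 says "peak plasma concentrations following a 40 mg dose occur 1-2 hours after administration" and "Plasma half-life of propranolol is 3-6 hours".

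**The concern.** The 60-minute sample is the only look at what propranolol does to IL-6 without stress, and it falls at the first minute of the stated peak window. The outcome samples come roughly two to three hours after dosing, still under drug exposure by the protocol's own half-life. With no unstressed group, a drug effect on IL-6 that develops after 60 minutes cannot be told apart from a smaller stress response.

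The same gap affects the placebo arm. A placebo rise over about three hours with a catheter in place, from an early-afternoon baseline (around 1:15 PM), has no unstressed comparison either. The between-arm contrast can also be significant when placebo shows no rise, in which case there was nothing to attenuate. At stake is the wording of the primary conclusion, and by extension the secondary ones, rather than the validity of the randomised comparison.

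**Working it through.** **The plan's own figure.** Section 6.4 gives 45 per condition; 2 x 45 = 90, and 90 + 5 extra = 95, as the synopsis has it. No effect size, SD, correlation or power is stated, so the power claim cannot be reproduced and every effect size below is an assumption.

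**1. Clock after dosing** (Section 4.1). Draw 2 at 60 min; recording 5 min; stress task 2 + 10 + 5 = 17 min.
- End of task: 60 + 5 + 17 = 82 min at the earliest.
- Post-stress draws: 82 + 30 = 112, 82 + 60 = 142, 82 + 90 = 172 min.
- Time to explain the task is not given. An assumed 20 min moves these to 132, 162 and 192.
- The first outcome draw is therefore at least 112 - 60 = 52 min after the drug-only check.

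**2. What the contrast estimates.** Let D(t) be the drug effect on IL-6 without stress, S(t) the stress response on placebo, A(t) the true attenuation, and C(t) catheter and time-of-day change. From 60 min to t:
- placebo change = C + S;
- propranolol change = C + S - A(t) + [D(t) - D(60)];
- difference = -A(t) + [D(t) - D(60)].

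The check estimates D(60) only. If baseline is dropped, D(60) is removed but D(t) - D(60) stays. If both pre-stress samples are kept as an equally weighted reference, D(t) - D(60)/2 stays. Neither branch isolates A(t). The placebo rise estimates C + S, not S.

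**3. Size for a single pre-to-post contrast.** Set A = 0 and let the drug-only fall be d SD of the change score. With 45 per arm, a two-sided 5% t-test (88 df, critical value 1.987) has noncentrality d x sqrt(45/2) = 4.743d.

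| d | noncentrality | P(significant, favouring propranolol) |
|---|---|---|
| 0 | 0 | 2.5% |
| 0.2 | 0.949 | 15% |
| 0.3 | 1.423 | 29% |
| 0.4 | 1.897 | 47% |

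**4. The two-step plan, simulated.** 45 per arm, five time points, random intercept, zero true attenuation, 3,000 runs per scenario; effects here are in SD of a single measurement and the main test is the undirected condition-by-time F-test. For a drug-only fall starting after 60 min, the check is significant in 4-6% of trials, its nominal rate. The main test is significant as follows:

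| Fall | correlation 0.5 | 0.7 | 0.9 |
|---|---|---|---|
| 0.2 SD | 16% | 27% | 73% |
| 0.3 SD | 37% | 59% | 98% |
| 0.5 SD | 82% | 97% | >99% |

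With no drug effect it is 4-5%. If a quarter of the effect is already present at 60 min, the check flags it in 6-26% of trials and the main test is significant in 11-98%.

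**5. Effect of requiring a placebo rise.** Add to step 3 the condition that the 95% CI for the placebo change lies above zero. If placebo does not change, that condition is met in only 2.5% of trials, so false attenuation cannot exceed 2.5%; simulation gives about 2% in place of 15-47%. If placebo rises by 0.5 SD of the change from any cause, the condition is met in about 91% of trials and false attenuation stays at about 15%, 29% and 46%. The condition is useful but not sufficient.

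**The case against.** The strongest reply is that nothing in the documents shows propranolol lowers IL-6 without stress. For a false reading, such an effect must exist, point downward, emerge after 60 minutes and reach significance. Section 1.3 gives plasma levels only, which does not show that an IL-6 effect is still to come. This stands. A reader might infer that a late drug effect *will* be reported as attenuation; the documents support only that it *could* be, and an upward effect would hide real attenuation.

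Second, Section 6.1 limits the check to the period before stress and uses it only to choose which pre-stress samples enter the model. It never claims to exclude a drug-only effect later. That is fair, so the criticism is not that the plan misdescribes its check. It is that nothing else in the plan fills the gap, while the main result is still read in stress-specific terms.

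Third, the hypothesis already includes a placebo rise, and Section 6 says results above p = .05 will not be interpreted, so a non-significant placebo rise could not itself be claimed. This partly answers the no-response case. What is missing is a link between the two parts: the arm contrast can be significant, and be glossed as a prevented rise, whatever placebo did.

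Fourth, a placebo rise could come from the catheter or the clock, so making it the licence for claiming attenuation would be inconsistent. That is right, and it is why the condition can only be necessary, with the wording of the conclusion doing the rest.

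**Conclusion.** The concern holds as a limit on interpretation. Both arms are stressed, the one drug-only IL-6 check is at 60 minutes, and the outcome draws are at about 112 minutes or later, so the plan cannot separate a later stress-independent drug effect from attenuation under either branch of the check. A reader might go further and infer that the trial's comparison is invalid; it is not. The randomised propranolol-placebo contrast in post-stress IL-6 is sound, and only its stress-specific reading is unidentified.

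The size depends on assumptions: for a drug-only fall of 0.2-0.4 SD of the pre-to-post change, about 15-47% of trials would favour propranolol with no true attenuation, against 2.5% under the null. The documents give no evidence on whether such a fall occurs, and the figures change with the contrast, the correlation and the share of the effect present at 60 minutes. The point is worth correcting before analysis because it concerns the primary conclusion and costs only text.

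**What to change.** Amend Section 6.1, and Section 6.2 by reference with the expected direction of placebo change stated for each outcome:

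1. **Necessary condition.** Do not describe the result as attenuation unless the placebo pre-to-post IL-6 rise has a 95% CI above zero and the condition-by-time contrast favours propranolol. If only the contrast is met, report lower IL-6 after propranolol.
2. **Wording that governs in all cases.** Even when both hold, conclude that propranolol reduced the rise in IL-6 seen after the TSST. State that, with no unstressed group, the 60-minute test does not exclude a drug-only, catheter or time-of-day contribution at the post-stress draws.

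The cost is a narrower claim and one added condition; no samples, participants or procedures change. Identifying a stress-specific effect would need unstressed groups. For scale, 45 per arm detects (1.960 + 0.842) x sqrt(2/45) = 0.59 SD at 80% power. A drug-by-stress interaction of that size in a 2 x 2 design has twice the variance at a given cell size, so it needs about 90 per cell, or 360 in total. Section 6.4 says there are no grant funds for additional participants, so the wording change is the realistic remedy.
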